6.3 MEASURES TO MINIMIZE BIAS: RANDOMIZATION AND BLINDING

Each patient will be assigned a unique study ID. Patients will be assigned to an arm by drawing lots. This will be done by preparing 20 opaque, sealed envelopes. 10 of these envelopes will contain the word "Experimental," and the remaining 10 will contain the word "Control." On Day 0 of the study period, each participant will choose an envelope at random, and be assigned to that arm. This technique will ensure that the ratio between patients in each arm is 1:1.

To minimize bias, the outcomes assessor, who is an advanced practice physiotherapist clubfoot provider, will be independent of the study and design teams and blinded, so they will not know which bar has been assigned to which patient.

To ensure that the outcomes assessor remains blinded, a member of the study team will check in the patient at the beginning of each visit, remind the patient and parent about the blinding, and ensure that the bar is removed and hidden from view before the outcome assessor enters the evaluation room.

Unblinding may occur for any participant who has experienced an adverse event, such as clubfoot recurrence, and must return to their original SB, if not already using it. Unblinding will occur for all participants if any severe adverse event occurs that is related to the use of the DB. For unblinding to occur, the outcomes assessor must notify a member of the study team, and any member of the study team may unblind the outcomes assessor.

All intentional and unintentional breaking of the blind will be documented in the study's enrollment log, along with the reason(s) for unblinding. Per protocol, the Data Safety Monitoring Board and Research Ethics Board will also be notified of any adverse events or unblinding.

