9 STATISTICAL CONSIDERATIONS

9.1 SAMPLE SIZE DETERMINATION

The intent of this study is to obtain preliminary data on the current prototype and evaluate the feasibility of conducting a larger-scale clinical trial. Therefore, only a minimum of 10 patients will be enrolled in each arm.

In a future effectiveness randomized controlled trial, we plan to use a sample size of 124, with 62 patients per arm. This sample size will ensure that the study has sufficient statistical power to detect a minimal clinically detectable difference in recurrence rates of at least 20% between the SB and DB group. Note this is assuming that the recurrence rates in the control arm will be 30%, as reported recurrence rates after correction range from 20-41% (6). This power analysis was conducted based on 80% power and 5% type 1 error.

The Clubfoot Clinic at SickKids sees approximately 35 patients per week. Based on the frequency of clinical visits required for patients at different stages in the Ponseti treatment, it is expected that approximately 15% of these patients will be between the ages of 1 and 3 and in the minimum 12-hour per day bracing stage of the Ponseti treatment. Furthermore, approximately 80% of all clubfoot patients are idiopathic, and it is expected that 75% of eligible patients will be willing to participate in the trial (22). Therefore, it is foreseen that it will take approximately 2 months to register all 20 participants.

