9.2 POPULATIONS FOR ANALYSES

The following study populations are defined and will be analyzed as specified below:

- Intent to treat population: the total population of patients registered in the study.
- Experimental arm population: all registered participants in the experimental arm with DB.
- Control arm population: all registered participants in the control arm with SB.

- Safety population: all registered participants who wore their FAB as prescribed for the full 90-day study period.
- Brace discomfort population: all registered participants who have any history of brace intolerance or indicated in the parent-reported survey that they are not comfortable/have concerns with their original FAB.
- Brace comfort population: all registered participants who have no history of brace intolerance and indicated in the parent-reported survey that they are comfortable/have no concerns with their original FAB.

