9.3.3 ANALYSIS OF THE SECONDARY ENDPOINTS

Parent-reported comfort levels will be determined by parent-reported surveys with 5-point Likert scale responses. Results from these surveys will be analyzed with descriptive statistics for the intent to treat population, the brace discomfort population, and the brace comfort population.

Daily bracing times will be measured by a temperature sensor added in each patient's boots for the entire 90-day study period. The number of hours the brace is worn per day will be divided by the standard number of desirable hours in brace (12 hours) in order to obtain a fraction that quantifies the patient's adherence to the FAB. Mean 'adherence fractions' will be calculated for patients in each arm, and then compared using descriptive statistics. This analysis will be performed for the intent to treat population, the brace discomfort population, and the brace comfort population. This data will be compared to the self-reported brace wear hours by parents in their daily logs.

To ensure minimal efficacy of the DB prototype, all signs of clubfoot recurrence will be carefully examined at each study visit. The null hypothesis is that 'the dynamic bar does not lead to higher rates

of clubfoot recurrence,' and it will be rejected if the number of patients in the safety population that develop clubfoot recurrence during the 90-day study period, is substantially greater in the experimental arm than it is in the control arm (i.e. more than 2 instances of clubfoot recurrence in the experimental arm than in the control arm). Note that this endpoint is not intended to prove safety or efficacy, but rather to ensure that the design may prevent early recurrence before a larger-scale trial is conducted. Clubfoot recurrence is defined as a Pirani score > 0.5, a new occurrence of cavus, adduction and/or hindfoot varus, or a loss of passive ankle dorsiflexion (equinus) of < 10 degrees above neutral or a reduction of 5 or more degrees from the previous visit. Note that all clinical tests required to diagnose recurrence are routinely performed as standard clubfoot care.

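### With about 10 children per arm, not meeting the more-than-2 recurrence rule is inconclusive and cannot reassure about recurrence with the dynamic bar

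*Combined protocol and SAP*

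**What the plan says.** Section 9.3.3 of the combined protocol and SAP opens the recurrence analysis with a purpose: "To ensure minimal efficacy of the DB prototype, all signs of clubfoot recurrence will be carefully examined at each study visit". It then states a null hypothesis that the DB does not raise recurrence, and a rejection rule that begins "it will be rejected if the number of patients in the safety population that develop clubfoot recurrence during the 90-day study period". The excess on the DB that triggers rejection is spelled out as "more than 2 instances of clubfoot recurrence in the experimental arm than in the control arm". The section gives no significance level, power or reason for the cut-off.

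It adds a disclaimer about purpose: "not intended to prove safety or efficacy, but rather to ensure that the design may prevent early recurrence before a larger-scale trial is conducted".

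The rule applies to the safety population, defined in Section 9.2 as "all registered participants who wore their FAB as prescribed for the full 90-day study period". On numbers, Section 9.1 says "Therefore, only a minimum of 10 patients will be enrolled in each arm", and Section 4.1 stops recruitment once each arm has 10. Section 9.3.1 describes the whole analysis as descriptive because the sample is small. It lists means, standard deviations and percentile ranks, but no confidence intervals.

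**The concern.** The burden of proof points the wrong way for a risk check. The favourable statement is the null, and it stands unless the data show a sizeable excess. The smaller the sample, the more often it stands, whatever the truth.

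The likely result is therefore that the null is not rejected. A reader could take that as evidence that the DB does not raise recurrence, which is the risk that Sections 2.3 and 8.2.3 say may be higher with it. The plan offers no interval to show how large an increase the data leave open. The disclaimer rules out proof, but the same sentence goes on to say the endpoint will ensure something before the larger trial, and the two-way conclusion stays in place.

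**Working it through.** **Inputs**
- Rule: flag if DB recurrences minus standard-bar (SB) recurrences are 3 or more (Section 9.3.3).
- 10 children per arm, allocated 1:1 (Sections 4.1, 6.3 and 9.1).
- Yardstick for size: the 20-point difference used to plan the future trial (Section 9.1).
- SB recurrence over 90 days: not given. The 30% in Section 9.1 (range 20% to 41%) is a rate after correction with no 90-day window. I assume 0% to 30%.
- Non-adherence: 35% on average (Section 2.2). That it applies here is an assumption.

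**1. The plan's own figure.** The only powered calculation is the future trial's 62 per arm. Reading it as 30% against 10%, with two-sided 5% error and 80% power:

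n = [1.960 × √(2 × 0.20 × 0.80) + 0.842 × √(0.30 × 0.70 + 0.10 × 0.90)]² / 0.20² = (1.109 + 0.461)² / 0.04 = 61.6, so 62 per arm.

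It reproduces. It fits a fall from 30% to 10%; a rise from 30% to 50% would need 93 per arm. So 20 points is borrowed here as a size of interest. The plan does not call it a harm margin.

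**2. How often the rule flags.** For independent binomial counts,

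P(flag) = Σ over c of P(SB count = c) × P(DB count ≥ c + 3).

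Example, SB 10% and DB 30%, 10 per arm:
- c = 0: 0.3487 × 0.6172 = 0.2152
- c = 1: 0.3874 × 0.3504 = 0.1357
- c = 2: 0.1937 × 0.1503 = 0.0291
- c ≥ 3: 0.0028
- Total 0.383

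The same sum over the assumed range gives:

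| True DB excess | SB 0% | SB 5% | SB 10% | SB 20% | SB 30% |
|---|---|---|---|---|---|
| 0 points (false alarm) | 0% | 0.7% | 3.0% | 7.8% | 11.0% |
| 10 points | 7% | 12% | 17% | 22% | 24% |
| 20 points | 32% | 36% | 38% | 40% | 41% |
| 30 points | 62% | 61% | 61% | 60% | 60% |
| 40 points | 83% | 81% | 79% | 78% | 77% |

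The chance of flagging reaches one half at an excess of about 25 points. The false-alarm rate is not fixed by the rule; it moves with the unknown SB rate.

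**3. Effect of the analysis set.** If 35% of children fall out, 10 × (1 − 0.35) = 6.5 per arm remain. For DB 30% and SB 10%, the chance of flagging falls from 38% to 22% with 7 per arm and 16% with 6.

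**4. What a non-rejecting result leaves open.** Newcombe 95% limits for the difference D, built from the Wilson limits (l, u) of each arm, are

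lower = D − √[(p_DB − l_DB)² + (u_SB − p_SB)²]; upper = D + √[(u_DB − p_DB)² + (p_SB − l_SB)²].

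For 2/10 against 0/10, the Wilson limits are 0.057 to 0.510 and 0 to 0.278:
- lower = 0.20 − √(0.143² + 0.278²) = −0.11
- upper = 0.20 + 0.310 = +0.51

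Other results that are not rejected:
- 0/10 against 0/10: −28 to +28 points
- 1/10 against 0/10: −19 to +40 points
- 3/10 against 1/10: −16 to +51 points

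None of these excludes a 20-point increase.

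**The case against.** The strongest reply is that the documents already admit the weakness. Section 9.3.3 disclaims proof, Section 3 says 20 participants cannot establish safety or efficacy, and Section 4.2 says a difference in effectiveness is unlikely to be found with at most a month on the DB. That stands, and it lowers the weight of the point. It does not remove it: a rule that is expected not to fire cannot ensure anything, and the null and rejection wording conflicts with the descriptive approach in Section 9.3.1.

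A reader might infer that non-rejection is a gate to the larger trial. The documents do not say so. Feasibility rests on recruitment and retention (Section 4.1), recurrence is the third secondary endpoint, and Section 4.2 plans the larger trial without a recurrence condition. The phrase about what is ensured before that trial invites the inference but states no decision rule.

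A reader might also infer that the rule misses harmful differences of any size. It does not: it misses more often than not only below about 25 points, and as an alert for gross failure it has some value.

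Nor is it the only safeguard. Recurrence is examined at every visit, a monitoring board reviews data by arm (Section 10.1.4), and the study can be stopped for unacceptable risk without this threshold being reached (Section 10.1.1). Those protect children during the trial; they do not change what may be concluded from non-rejection afterwards.

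**Conclusion.** The point holds in this form: not rejecting the null cannot serve as reassurance about recurrence. Under assumed SB rates of 0% to 30% and 10 per arm, a true 20-point excess goes unflagged 59% to 68% of the time, and even a result with no recurrences in either arm is compatible with an increase of 28 points. The detection figures rest on assumed 90-day rates and independent children. The intervals depend only on the counts and 10 per arm. Using 10 per arm favours the plan, because the rule counts only adherent children.

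The fault lies in how a secondary endpoint is framed and reported. Given the disclosures and the absence of a formal progression rule, the change should be made but ranks at the low end of importance.

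**What to change.** In Section 9.3.3:
- Delete the null hypothesis and the rejection wording, in line with Section 9.3.1.
- Keep the more-than-2 threshold only as a one-way alert. Print beside it the chance of flagging and of a false alarm over a stated range of assumed rates.
- Report recurrences per arm, and the difference between arms, with 95% confidence intervals in all randomised children.
- State that an excess below 3 is inconclusive and is not evidence of no increase.

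This needs no extra children, visits or measurements: only revised wording, a small table and a few intervals. The price is that the trial's stated conclusion on recurrence becomes less favourable.

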2.2 STUDY RATIONALE

This study seeks to evaluate the feasibility of conducting a large-scale clinical trial to evaluate the effectiveness of a newly designed dynamic bar (DB) for foot abduction bracing in clubfoot treatment (see photos in Appendix A). This DB fixes the foot and ankle position relative to two L-shaped brackets at the end of each bar, in order to maintain a corrective foot position at all times during use and prevent over-activation of deforming muscles. It allows independent extension and flexion the knees and hips while restricting motion of the ankle into plantarflexion or inversion as the latter movements may

contribute to muscle imbalance or recurrence of the clubfoot deformity. It is hypothesized that this added leg mobility would reduce brace intolerance and improve child comfort without increased risk of recurrence.

Brace non-compliance is the leading cause of clubfoot recurrence (6,7). Reported recurrence rates after correction range from 20-41% and are higher the earlier the brace is discontinued (6). According to the Ponseti International website, the rate of recurrence when brace wear stops in the first year is 90%, 70–80% in the second year, 30–40% in the third, 10–15% in the fourth, and approximately 6% in subsequent years. (3) Intolerance and non-adherence to bracing affects an average of 35% of patients and can increase recurrence rates by anywhere 5- to 17-fold (3,6,7,8). The large variation in reported brace intolerance and clubfoot recurrence can be attributed to the lack of consensus regarding the definitions of 'clubfoot recurrence' and 'non-compliance' to bracing, as well as variation in the prescribed bracing schedules (7,9).

Brace compliance and actual brace-wear hours are very challenging to assess, and most studies only include parent-reported wear schedules (7). Studies have shown that parents tend to over-report daily brace wear times. To address this, we will use a small temperature sensor placed in each patient's boots. These sensors have been used in past studies to provide objective measurements of daily bracing wearing times by measuring the temperature increase when the child is in the brace (10, 11,12). Automating the recording of daily brace wear will reduce human error and enable the study's endpoints to be assessed more accurately.

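### The recurrence rule in 9.3.3 judges a null about rates by a raw difference in counts, so its result depends on how many children in each arm happen to qualify

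*Combined protocol and SAP*

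**What the plan says.** Section 9.3.3 sets a null that "the dynamic bar does not lead to higher rates" of recurrence. This null is to be "rejected if the number of patients in the safety population that develop clubfoot recurrence during the 90-day study period" is clearly larger with the DB, and the section spells that out as "more than 2 instances of clubfoot recurrence in the experimental arm than in the control arm". Rejection therefore needs a DB count at least 3 above the SB count.

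Section 9.2 defines the population for the rule as "all registered participants who wore their FAB as prescribed for the full 90-day study period".

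The arms are equal only at allocation. Section 9.1 says: "Therefore, only a minimum of 10 patients will be enrolled in each arm". Section 6.3 says of the envelope draw: "This technique will ensure that the ratio between patients in each arm is 1:1".

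Neither 9.2 nor 9.3.3 gives a denominator, an expected or minimum size for the safety population, a wear cut-off for qualifying, or a provision for unequal arms. Section 9.3.3 does disclaim any proof of safety or efficacy, and 9.3.1 makes the analysis descriptive.

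**The concern.** A difference in counts can stand in for a difference in rates only if both arms supply the same number of children. Here the number supplied is itself an outcome, because a child enters the safety population by wearing the brace as prescribed for 90 days. The protocol hypothesises that wear differs between the bars (1.1, 4.1), so unequal arms are what the plan itself leads one to expect.

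Two things follow. If more DB than SB children qualify, the rule can reject although the DB rate is no higher. If few DB children qualify, the rule loses the ability to reject, and with two or fewer it has none. The second matters more: a poorly worn DB would be the hardest to flag, although 8.2.3 anticipates a raised recurrence risk with the DB and 9.3.3 places this check before a larger trial. A result of not rejected could then be read as reassurance when it reflects only a small arm.

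**Working it through.** **The plan's own figure.** No error rate is given for the recurrence rule. The only powered figure is the future trial's 62 per arm (9.1). With 30% v 10%, two-sided 5% and 80% power, n = [1.960·√(2·0.2·0.8) + 0.8416·√(0.3·0.7 + 0.1·0.9)]² / 0.2² = (1.109 + 0.461)² / 0.04 ≈ 61.6, so 62. It reproduces but has no bearing on this rule.

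**Inputs.**
- Threshold: DB count minus SB count ≥ 3 (9.3.3).
- Allocation: 10 per arm (6.3, 9.1).
- Proportion qualifying: not given. Section 2.2 reports that "Intolerance and non-adherence to bracing affects an average of 35% of patients", and 2.1 gives up to 61%. As assumptions, 65% and 39% qualify, independently and equally in both arms.
- Recurrence over 90 days: not given. The 30% in 9.1 is the control rate for the future trial, which 4.2 plans over at least two years. The rates below are illustrative, and children are taken as independent.

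**Step 1: observed tables.** Listing all tables with 1 to 10 children per arm:
- Equal observed rates, rule rejects: 5/10 v 2/4 (5 − 2 = 3; 50% each), 6/10 v 3/5 (60% each).
- Lower DB rate, rule rejects: 4/10 v 1/2 (4 − 1 = 3; 40% v 50%).
- Two or fewer DB children: the difference is at most 2, so the rule cannot reject even if all of them recur.

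**Step 2: probability of firing.** For fixed arm sizes, P = Σ Bin(e; n_DB, p_DB) · Bin(c; n_SB, p_SB) over all e − c ≥ 3.

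For 6 DB v 10 SB at 40% v 10%, each term is P(e DB recurrences) × P(at most e − 3 SB recurrences), for e = 3 to 6: 0.2765·0.3487 + 0.1382·0.7361 + 0.0369·0.9298 + 0.0041·0.9872 = 0.236. For 4 v 7: 0.1536·0.4783 + 0.0256·0.8503 = 0.095.

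| DB v SB children | 40% v 10% | 30% in both |
|---|---|---|
| 10 v 10 | 61.1% | 11.0% |
| 6 v 10 | 23.6% | 1.9% |
| 4 v 7 | 9.5% | 0.9% |
| 2 v 10 | 0% | 0% |

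In the other direction, at 30% in both arms, 10 DB v 6 SB gives 23.7%. At 5% in both arms the rule fires about 1% of the time or less at any sizes up to 10.

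Some of the lost sensitivity comes from small arms as such. At 30% v 10% the rule fires 38.3% at 10 v 10, 16.2% at 6 v 6 and 11.9% at 6 v 10. A threshold of 3 events is a 30-point difference with 10 per arm but a 50-point difference with 6 per arm.

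**Step 3: how often arms are small or unequal.** With n_DB ~ Bin(10, q), P(n_DB ≤ 2) is:
- q = 0.65: 0.00003 + 0.00051 + 0.00428 = 0.5%.
- q = 0.39: 0.0071 + 0.0456 + 0.1312 = 18.4%.

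The arms differ by 3 or more children in 24% (q = 0.65) or 25% (q = 0.39) of trials. Averaged over arm sizes, the 40% v 10% harm is flagged in 36% and 15% of trials respectively, against 61% at 10 v 10.

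**Step 4: would a cutoff on proportions repair it?** A difference in proportions above 0.20 is the same rule at 10 v 10. Averaged over arm sizes at q = 0.65, with an arm of zero counted as not firing:

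| True rates | Count rule | Proportion > 0.20 |
|---|---|---|
| 30% in both | 7.6% | 21.7% |
| 10% in both | 1.3% | 9.6% |
| 40% DB v 10% SB | 36% | 65% |

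With four or fewer DB children, one DB recurrence against none on SB already exceeds 0.20 (1/4 = 0.25). Much of the gained sensitivity comes from this lower bar.

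**The case against.** The strongest defence is that the stakes are small. Section 9.3.3 says the endpoint does not prove safety or efficacy, the analysis is descriptive, and no stopping or go/no-go decision is tied to the rule. Recurrence is also examined at every visit (1.3), and a DSMB reviews data by arm (10.1.4). This stands and limits the weight. It does not remove the mismatch: the text still names a null and a rejection criterion, and the criterion does not measure what the null states.

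A second defence is that the root cause is the wear-defined population. Allocation is 10:10, and children who miss any of visits 1 to 3 are replaced (7.2), so among all randomised children counts and rates would nearly coincide. That is largely right. Late losses could still make the arms unequal, and 9.3.3 as written uses the safety population.

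Three stronger readings are tempting, and the documents do not support them.
- A reader might infer that the rule will often raise false alarms. Sizes such as 10 v 6 need a large DB wear advantage: with 65% qualifying in both arms, 10 DB with 6 or fewer SB children occurs in 0.7% of trials. The 30% rate is not a 90-day figure, and at 5% false firing is about 1% or less.
- A reader might infer that the rule will usually be unable to fire. At the cited average non-adherence, two or fewer DB children has probability 0.5%. The 18% belongs to the cited upper figure. Section 5.2 excludes children with a current complaint of significant intolerance, so neither figure need apply here.
- A reader might infer that the same threshold on the proportion scale is the cure. Step 4 shows that it fires more often at equal rates, and it is undefined if an arm is empty.

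**Conclusion.** The point holds. The null is about rates, the rule is about counts, and no other section supplies a denominator. That the rule can reject at an equal or lower observed DB rate, and cannot reject with two or fewer DB children, is arithmetic and needs no assumption.

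The sizes do rest on assumptions: independent children, illustrative recurrence rates, and 39% to 65% qualifying. Within those, lost sensitivity is the main fault, with the chance of flagging a 40% v 10% difference falling from 61% to between 15% and 36% on average. False firing is the smaller one.

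Severity is minor to moderate, because the plan presents this as a screen. What changes is what the trial may conclude: a result of not rejected from small or unequal arms carries little information and should not be reported as a finding.

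**What to change.** In 9.3.3:
- Replace the count-based rejection with recurrence as x/n in each arm (children with recurrence / children assessed), and give the difference in proportions with an exact or score 95% confidence interval. Count children throughout, since the section now uses both patients and instances.
- Keep the count of more than 2 only as a signal, and only when all 10 children in both arms are assessed.
- State that no conclusion of not rejected is drawn from the count when arm sizes differ or fewer than 3 DB children are assessed.
- Keep the disclaimer on safety and efficacy.
- Do not adopt a fixed cutoff of 0.20 on the difference as a rejection rule.

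The cost is a few sentences and no new data. The intervals will be wide and the result will often be inconclusive; even 3/10 v 0/10, the weakest table that fires at full size, has a one-sided Fisher p of 0.105. If the analysis stays in the safety population, the count signal will in practice lapse: at 65% qualifying, all 20 children qualify with probability 0.65²⁰ ≈ 0.02%.
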